8.5.1 Safety Monitoring Rules for Liver Chemistry Tests

The following rules are adapted from the draft guidance for industry, "Drug-Induced Liver Injury: Premarketing Clinical Evaluation," issued by the U.S. Department of Health and Human Services, Food and Drug Administration, July 2009.

In the event of an ALT or AST measurement that is > 3 x the upper limit of normal (ULN) (or the greater of 2 x baseline value or 3 x ULN if the baseline value was > ULN), at any time during the study (treatment or post-treatment period), the initial measurement(s) should be confirmed as described above. Similarly, confirmatory measurements should also be performed if ALT or AST levels increase to 5 x ULN.

Frequency of Repeat Measurements: Patients with confirmed ALT or AST levels > 3 x ULN (or the greater of 2 x baseline value or 3 x ULN if the baseline value was > ULN), that are continuing to rise should have their liver chemistry tests (ALT, AST, ALP, INR, and total bilirubin) retested at least once-weekly until levels stabilize and begin to recover (ALT and AST levels become ≤ 1.2 x ULN or 1.2 x baseline value if the baseline value was > ULN).

Further Investigation into Liver Chemistry Elevations: For patients with confirmed ALT or AST levels > 3 x ULN (or the greater of 2 x baseline value or 3 x ULN if the baseline value was > ULN), the following evaluations should be performed:

- 1. Obtain a more detailed history of symptoms and prior and concurrent diseases
- 2. Obtain further history for concomitant drug use (including nonprescription medications, herbal and dietary supplement preparations), alcohol use, recreational drug use, and special diets
- 3. Obtain a history for exposure to environmental chemical agents and travel
- 4. Total, direct, and indirect bilirubin
- 5. Serology for viral hepatitis (HAV IgM, HBsAg, HCV antibody, HCV mRNA, CMV IgM, and EBV antibody panel)
- 6. Serology for autoimmune hepatitis (e.g., antinuclear antibody (ANA), antismooth muscle antibody, type 1 anti-liver kidney microsomal antibody)
- 7. Serum acetaminophen-protein adducts by high pressure liquid chromatography if recent acetaminophen usage by patient

Additional liver evaluations, including gastroenterology/hepatology consultations, hepatic CT or MRI scans, may be performed at the discretion of the Investigator, in consultation with the

Study Medical Monitor. Repetition of the above evaluations should be considered if a patient's ALT and/or AST levels reach 5 x ULN.

8.5.2 Safety Monitoring Rules for Renal Function

In the event of a confirmed (as described in Section 8.5) laboratory result meeting 1 or more of the following criteria, urinalysis (see Appendix B) will be required approximately every 2-3 weeks.*

- a. Creatinine clearance by CKD-EPI < 60 mL/min/1.73 m²
- b. Creatinine clearance by CKD-EPI decrease from baseline** > 25%
- c. Urine Alb/Cr ratio $> 5 \times \text{ULN}$
- d. Serum creatinine increase from baseline** > 0.5 mg/dL
- * Urine collection should be performed at the same time as the protocol specified collection of serum creatinine (see Appendices A and C)
- ** Baseline is the study CS3 Day 1 value

In addition, the first confirmed result meeting a criterion (at any time on study) will trigger an immediate evaluation by a local nephrologist, ideally within 1-week. The following labs should be obtained immediately: fasting serum creatinine, urine culture, 24-hour urine sample for creatinine clearance and urine protein, and urine microscopy sample with nephrologist's inspection of sediment. Consideration of a dose pause (for example with a confirmed CKD-EPI decrease > 25%) should be discussed with the Study Medical Monitor. A mandatory dose pause will occur with a 24-hour urine protein result of > 2.0 g.

If a patient remains stable over time they may be moved to less frequent monitoring of urinalysis at the discretion of the Study Medical Monitor in consultation with a nephrologist and the Investigator.

If a patient meets a renal monitoring rule that is confirmed on repeat testing, the Investigator should review the patient's concomitant medications for potentially nephrotoxic agents, and carefully consider discontinuing non-essential medications. Consultation with the Study Medical Monitor is encouraged.

8.5.3 Safety Monitoring Rules for Ocular Effects

All patients should receive an ophthalmology examination by an eye specialist at Weeks 26, 52, 78, 104, 130, and 156 and twice each subsequent treatment year (26th and 52nd week of each year). An ERG will also be performed at Weeks 78 and 156. In addition, any patient who complains of persistent ocular symptoms compatible with vitamin A deficiency (e.g., night blindness or dry eyes) should be referred for an ophthalmology examination. If the ophthalmologist confirms the patient's symptoms are consistent with vitamin A deficiency and/or the examination reveals physical findings that are consistent with vitamin A deficiency (but do not reach the stopping rule criteria described in Section 8.6.4) then an ERG examination should be conducted and analyzed by the central reader. In addition, it is suggested that a review

Amendment 5

of diet and supplement use and an evaluation for factors which may contribute to low vitamin A

If an ERG is changed from baseline and shows clear signs of vitamin A deficiency as assessed by the central reader and described below, then the patient should be monitored more frequently. Frequency will be determined by the Study Medical Monitor in consultation with the Investigator and ophthalmologist.

levels such as infection, alcohol consumption, and zinc and/or iron deficiency be conducted.

Clear signs of vitamin A deficiency as assessed by ERG include:

a. Change from baseline > 50%, and

Protocol

- b. Values below normal range (if baseline values were within normal range), and
- c. Changes that are approximately symmetrical between eyes (unless there is an alternative explanation for asymmetry)

Dosing with Study Drug may continue while these evaluations are being performed.

8.5.4 Safety Monitoring Rules for Platelet Count Results

Platelets will be monitored weekly throughout the treatment period and for a minimum of 6 weeks after the last dose of Study Drug (this includes early termination patients as well as patients that complete the full treatment period). For patients participating in the Post-Treatment Evaluation Period, frequency of testing after 6 weeks from the last dose of Study Drug will be determined by the Investigator in consultation with the Study Medical Monitor.

All platelet count results must be promptly reviewed by the Investigator to ensure that the count has not met the stopping rule

If for any reason there is more than 14 days between platelet values (e.g. lab report of an unreadable sample due to clumping, hemolysis, or quantity not sufficient, or a missed lab assessment), the Investigator will contact the patient to hold dosing until a new platelet value is obtained and reviewed.

If a patient's platelet counts fall below 100,000/mm³, additional lab tests may be requested as determined by the Investigator in consultation with the Study Medical Monitor.

Due to the 3 to 5-year study duration it is anticipated that patients may undertake travel including vacations, which may impede weekly platelet monitoring. In some situations it may be possible to arrange for local laboratory testing or use of the home healthcare service at their temporary location. The intent is to maintain weekly platelet monitoring and dosing where possible, as well as Investigator site contact with the study patients. However, if the above options are not possible, a temporary interruption of study treatment will be planned with a prompt blood draw upon the patient's return which must be reported and reviewed by the Investigator prior to the patient resuming dosing.

8.6 Stopping Rules

8.6.1 Stopping Rules for Liver Chemistry Elevations

In the event of confirmed laboratory results meeting the following criteria, and the event is without an alternative explanation as discussed with the Study Medical Monitor, dosing of a patient with ISIS 420915 will be stopped permanently:

- 1. ALT or AST $> 8 \times ULN$
- 2. ALT or AST > 5 x ULN at 2 consecutive weekly measurements (not less than 7 days nor more than 10 days apart) both of which are confirmed. Treatment with ISIS 420915 may continue until the second consecutive weekly ALT or AST measurement is confirmed to be > 5 x ULN
- 3. ALT or AST > 3 x ULN and total bilirubin > 2 x ULN
- 4. ALT or AST > 3 x ULN with the appearance of fatigue, nausea, vomiting, right upper quadrant pain or tenderness, fever, rash, and/or concomitant eosinophilia (> 5%)

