8.5 Safety Monitoring Rules

Please refer also to the "Guidance for the Investigator" section of the Investigator's Brochure.

In addition to the standard monitoring of clinical safety parameters, the following guidelines are provided for the monitoring of selected parameters chosen based on preclinical and clinical observations.

Confirmation Guidance: At any time during the study (treatment or post-treatment periods), the initial clinical laboratory results meeting the safety monitoring or stopping criteria presented below **must be confirmed** by performing measurements (ideally in the same laboratory that performed the initial measurement) on new specimens. All new specimen collections should take place as soon as possible (ideally within 3 days of the initial collection).

Stopping Rule Guidance: In the event of an initial clinical laboratory result that meets a stopping criterion, patients must not be re-dosed until a confirmatory test result has been reviewed by the Study Medical Monitor. If any of the stopping criteria described in Section 8.6 are met and are confirmed, the patient will be permanently discontinued from further treatment with ISIS 420915, evaluated fully as outlined below and in consultation with the Study Medical Monitor or appropriately qualified designee, and will be entered into the post-treatment evaluation period of the study (after completing the early termination [ET] assessments). In general, patients who do not meet the stopping rules based upon retest may continue dosing. However, the Investigator and the Study Medical Monitor (or appropriately qualified designee) should confer as to whether additional close monitoring of the patient is appropriate.

Additional Guidance: If possible, a pharmacokinetic sample should be collected as soon as possible after an SAE has occurred (preferably within 2 weeks). In addition, if a patient is asked

to return to the clinic for additional evaluations due to an AE, then a pharmacokinetic sample should be taken at the time of the unscheduled visit.

For all safety monitoring rules below "baseline" will be defined as the ISIS 420915-CS3 Day 1 value.

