9.5 Procedures for Handling Special Situations

9.5.1 Abnormalities of Laboratory Tests

Clinically-significant abnormal laboratory test results may, in the opinion of the Investigator, constitute or be associated with an AE. Examples of these include abnormal laboratory results that are associated with symptoms, or require treatment, e.g., bleeding due to thrombocytopenia, tetany due to hypocalcemia, or cardiac arrhythmias due to hyperkalemia. Whenever possible, the

underlying diagnosis should be listed in preference to abnormal laboratory values as AEs. Clinically-significant abnormalities will be monitored by the Investigator until the parameter returns to its baseline value or until agreement is reached between the Investigator and the Study Medical Monitor. Laboratory abnormalities deemed not clinically-significant (NCS) by the Investigator should not be reported as AEs. Similarly, laboratory abnormalities reported as AEs by the Investigator should not be deemed NCS on the laboratory sheet.

The Investigator is responsible for reviewing and signing all laboratory reports. The signed clinical laboratory reports will serve as source documents.

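### Liver stopping criterion 2 needs a second ALT/AST value at 7–10 days, but the protocol times that test only for patients whose values are still rising

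*Combined protocol and SAP*

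**What the plan says.** Protocol 8.6.1 lists four liver criteria for permanent discontinuation, each requiring confirmed results and no alternative explanation. Criterion 2 is the one for persistence: ALT or AST above 5 × ULN at two consecutive weekly measurements, "not less than 7 days nor more than 10 days apart) both of which are confirmed". It also permits dosing while the second value is awaited: "Treatment with ISIS 420915 may continue until the second consecutive weekly ALT or AST measurement is confirmed to be > 5 x ULN".

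The repeat-testing rule is in Protocol 8.5.1. Patients with confirmed ALT or AST above 3 × ULN (or the baseline-adjusted limit) "that are continuing to rise should have their liver chemistry tests (ALT, AST, ALP, INR, and total bilirubin) retested at least once-weekly", and this goes on "until levels stabilize and begin to recover", which the section defines as 1.2 × ULN or less (1.2 × baseline if baseline was above ULN). At 5 × ULN the section adds a confirmatory measurement and says of the diagnostic work-up: "Repetition of the above evaluations should be considered".

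Three other provisions bear on follow-up:

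- Protocol 8.5 times the confirmatory specimen: "ideally within 3 days of the initial collection".
- For patients who do not meet a stopping rule on retest, 8.5 says the Investigator and Study Medical Monitor "should confer as to whether additional close monitoring of the patient is appropriate".
- Protocol 9.5.1 says that clinically significant "abnormalities will be monitored by the Investigator until the parameter returns to its baseline value or until agreement is reached" with the Medical Monitor.

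**The concern.** Criterion 2 cannot be met without a liver test 7 to 10 days after the first value. The section that orders weekly tests makes them depend on trend. A patient seen to be rising is covered, because once weekly testing starts it continues through any plateau until recovery. A patient whose value is already flat or slightly lower at the confirmatory draw is not.

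That second patient may have exactly the persistent elevation that criterion 2 is written for. Dosing may continue, and whether it stops under this criterion depends on a site choosing to retest and on the retest falling on Days 7–10. Safety and tolerability are the primary objective. SAP 3.3.4 tabulates patients stopped under the liver rule, and a patient who was never retested in time cannot appear in that table under criterion 2.

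**Working it through.** The plan gives no figure to reproduce here. The check asks whether any provision supplies an ALT/AST value on Days 7–10 for a confirmed, non-rising value above 5 × ULN.

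**1. The text.**

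- *Confirmatory draw (8.5):* ideally by Day 3, too early to be the second weekly value.
- *Bar on re-dosing (8.5):* applies to an initial result that meets a stopping criterion. One value above 5 × ULN does not meet criterion 2.
- *Weekly retesting (8.5.1):* requires a rising value.
- *Discussion with the Medical Monitor (8.5), repeat work-up (8.5.1), monitoring of abnormalities (9.5.1):* none sets an interval.
- *Weekly visits (Appendix C):* platelets weekly and creatinine every 2–3 weeks, without ALT/AST.

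**2. The routine chemistry schedule.** Inputs are the chemistry row and visit windows in Protocol Appendix A, with Year 4–5 target days from SAP Appendix 3, Table 3.

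- Day 1 (no window)
- Days 22, 43, 64, 85, 99, 120, 141, 155, 176, 197, 267, 358 (±7)
- Days 449 to 1086 every 91 days (±10)
- Days 1177 to 1814 every 91 days (±14)

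That is 29 panels and 28 intervals. The possible range of an interval is its target gap ± (window of first visit + window of second visit). Weekly doses strictly between two pre-dose draws = floor((gap − 1)/7); for 91 days, floor(90/7) = 12, and 12 × 300 mg = 3,600 mg.

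| Interval | Number | Target gap (days) | Range with windows (days) | Can fall on 7–10? | Doses between draws over the range |
|---|---|---|---|---|---|
| Day 1–22 | 1 | 21 | 14–28 | No | – |
| Other 21-day gaps | 7 | 21 | 7–35 | By chance | – |
| 14-day gaps | 2 | 14 | 0–28 | By chance | – |
| Week 29–39 | 1 | 70 | 56–84 | No | – |
| Week 39–52 | 1 | 91 | 77–105 | No | 10–14 |
| Week 52–65 | 1 | 91 | 74–108 | No | 10–15 |
| Weeks 65–156 | 7 | 91 | 71–111 | No | 10–15 |
| Week 156 to Y4-W13 | 1 | 91 | 67–115 | No | 9–16 |
| Within Years 4–5 | 7 | 91 | 63–119 | No | 8–16 |

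At target days, 0 of 28 intervals are 7–10 days; the shortest is 14. With windows, 7 + 2 = 9 can be, all between Weeks 4 and 29. None of the 1 + 17 = 18 intervals after Week 29 can be; the shortest possible is 56 days.

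**3. An example on target days.** The first value above 5 × ULN is drawn at Week 52, Day 358, and confirmed by Day 361 without a rise. Criterion 2 needs a second value on Days 365–368. The next scheduled chemistry panel is Day 449, 449 − 358 = 91 days after the first. Weekly doses fall on Days 365, 372, …, 442: (442 − 365)/7 + 1 = 12 doses. The Day 449 value is outside Days 7–10, so it cannot complete the pair; at most it starts a new one. The Week 53 platelet visit, by contrast, has a target of Day 365, exactly 7 days after the first value.

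**The case against.** The strongest reply is that criterion 2 already names the test. It speaks of consecutive weekly measurements with a stated spacing and ties the permission to dose to the second of them, so an investigator applying it would see that a one-week repeat is needed. A careful site may well do this. The wording is still a condition for stopping, however; it does not instruct anyone to draw blood.

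Second, 8.5.1 does not define a continuing rise. Judged against the last routine panel, a patient newly above 5 × ULN has risen, and on that reading weekly testing starts. Judged between the initial and confirmatory draws, it does not start. The text supports either reading, and a stopping rule should not depend on which one a site adopts.

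Third, the response to a confirmed elevation is not all optional. For any confirmed value above 3 × ULN, rising or not, 8.5.1 calls for history, drug and alcohol review, bilirubin, and viral and autoimmune serology. Protocol 8.7 allows dose pauses for adverse events, and 8.8 requires discontinuation when an adverse event necessitates it. These are real protections, and the bilirubin result informs criterion 3. None of them includes a timed repeat of ALT/AST.

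Three limits stand. A value clearly falling at confirmation has less need of weekly tests than a plateau. The schedule figures describe what happens only if no unscheduled liver test is taken. The Investigator's Brochure guidance and the Safety Management Plan, to which the protocol refers, are not among the documents and could set a retest interval.

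**Conclusion.** The concern holds. Followed literally, 8.5.1 leaves criterion 2 without its second value for a confirmed ALT/AST above 5 and up to 8 × ULN that is not rising at confirmation, with bilirubin no more than 2 × ULN and none of the criterion 4 signs. Criteria 1, 3 and 4 still protect patients outside that range.

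Routine panels can supply the value only by accident of scheduling in 9 early intervals, and not at all after Week 29. The 91-day interval and 12 doses are the consequence at target days if no extra test is ordered; they are not a forecast of what sites will do. The conclusion assumes that the trend is judged at the confirmatory draw and that the unseen documents do not set the interval.

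The gap is narrow and its frequency unknown, so this is a change that should be made rather than a fundamental defect. Confidence is medium.

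**What to change.** Add to Protocol 8.5.1: after any confirmed ALT or AST above 5 × ULN, whether or not it is rising, repeat liver chemistry 7 to 10 days after the first value and then weekly for as long as it stays above 5 × ULN, drawn at the existing weekly platelet visit. Confirmation of the second value then follows 8.5 as written.

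Optionally, if the repeat is not available by Day 10, hold dosing until it has been obtained and reviewed. Protocol 8.5.4 already does this when more than 14 days pass between platelet values.

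The cost is one sentence in an amendment and one extra chemistry tube per week, at a visit already scheduled, for affected patients only. The optional hold would delay a few doses when a retest is late.

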8.6.2 Stopping Rules for Renal Function Test Results

In the event of an estimated creatinine clearance by CKD-EPI meeting any of the following criteria, a serum creatinine and 24-hour urine sample for creatinine clearance and protein should be obtained:

- CKD-EPI decrease of > 50% from baseline*
- Value $< 45 \text{ mL/min/}1.73 \text{ m}^2 \text{ (if baseline CKD-EPI} <math>> 60 \text{ mL/min/}1.73 \text{ m}^2 \text{)}$
- Value $< 30 \text{ mL/min/1.73 m}^2$ (if baseline CKD-EPI $\le 60 \text{ mL/min/1.73 m}^2$)

Dosing of a patient with ISIS 420915 will be stopped permanently if the 24-hour urine testing confirms any of the following values in the absence of an alternative explanation agree by a consulting nephrologist:

- urine protein is > 3.5 g
- creatinine clearance < 45 mL/min/1.73 m² (if baseline CKD-EPI > 60 mL/min/1.73 m²)
- creatinine clearance < 30 mL/min/1.73 m² (if baseline CKD-EPI ≤ 60 mL/min/1.73 m²)

Irrespective of whether the stopping rule is confirmed or not, the follow-up schedule and frequency of renal function monitoring after the initial event will be determined by the Study Medical Monitor in consultation with the Investigator and a renal consult will be requested.

8.6.3 Stopping Rule for Platelet Count Results

In the event of a confirmed platelet count less than 75,000/mm³, and in the presence of major bleeding or clinically-relevant non-major bleeding (defined below; Schulman et al. 2005), dosing of a patient with ISIS 420915 will be stopped permanently. The follow-up schedule for any

^{*} baseline is study CS3 Day 1 value

events meeting this stopping criterion will be determined by the Investigator in consultation with the Study Medical Monitor.

In the event of a confirmed platelet count less than $75,000/\text{mm}^3$, and in the absence of major bleeding or clinically-relevant non-major bleeding, further dosing of a patient with ISIS 420915 must be held until the platelet count returns to at least $100,000/\text{mm}^3$. Weekly platelet monitoring should continue during this period. In addition, the Investigator should give consideration to collecting duplicate platelet samples for study in a local lab in parallel to the central lab if it would provide quicker access to the patients platelet count. If the platelet count was confirmed to be $< 50,000/\text{mm}^3$, then monitoring should be increased to daily until two successive values show improvement. The Investigator must notify the Study Medical Monitor within 24 hours of any local lab platelet results that show a level $< 50,000/\text{mm}^3$.

The suitability of the patient for continued dosing and the need for any modification to treatment schedule or dose (refer to Section 8.7) will be determined by the Investigator in consultation with the Study Medical Monitor and will be based on factors such as the original rate of decline in the patient's platelet count, whether any bleeding events were experienced by the patient, and the speed of recovery of platelet count upon holding of dosing.

Definition of major bleeding events:

International Society on Thrombosis and Haemostasis (ISTH) Major Bleeding:

- 1. Fatal bleeding, and/or
- 2. Symptomatic bleeding in a critical area or organ, such as intracranial, intraspinal, intraocular, retroperitoneal, intraarticular or pericardial, or intramuscular with compartment syndrome, and/or
- 3. Bleeding causing a fall in hemoglobin level of 20 g/L (1.24 mmol/L) or more within 24 hours, or leading to transfusion of 2 or more units of whole blood or red cells

Definition of clinically-relevant, non-major bleeding events:

- 1. Multiple-source bleeding
- 2. Spontaneous hematoma $> 25 \text{ cm}^2$
- 3. Excessive wound hematoma (not injection site related)
- 4. Macroscopic hematuria (spontaneous or lasting > 24 hours if associated with an intervention)
- 5. Spontaneous rectal bleeding; epitasis, gingival bleeding, hemoptysis, hematemesis
- 6. Bleeding after venipuncture for > 5 minutes

